3.6 Secondary Endpoints

- Participant satisfaction on a Likert Scale of 1 - 10 (10 = Completely satisfied and 1 = Completely Dissatisfied) after the Office Cystoscopic Onabotulinum Toxin A injection (collected 5-10 minutes after the procedure)
- Depression Screen Score (PHQ 9)
- Anxiety Screen Score (GAD 7)
- History of Sexual Abuse
- History of Chronic Pelvic Pain
- Participant Demographics: Age, Ethnicity, Basal Metabolic Index (BMI), Insurance
- Co-morbid conditions
- Current Medications
- Smoking Status
- Past or Current Illicit Drug Abuse
- Presence of Chronic Pain
- Number of Previous Onabotulinum Toxin A injection
- Previous Therapies for OAB (Lifestyle, Medication, Peripheral Tibial Nerve Stimulation, Sacral neuromodulation)

Source: The Participant Satisfaction Score, PHQ 9 score and GAD 7 score will be documented by the study coordinator into the case report forms and later transferred in the REDCap Data Management system. The participant demographics, co-morbid condition, current medications, smoking status, history of past or current illicit drug abuse, presence of chronic pain, number of previous Onabotulinum Toxin A injections, and previous therapies for OAB will be extracted from the electronic medical records. This information will be transferred to the REDCap Data Management System by the Principal and Co-investigators on the study.

4 Subject Selection Enrollment and Withdrawal

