Interpretation: Assuming that pain as measured is decreased in the Active TENS group when compared to the placebo TENS group, then we will accept our hypothesis. If not, we will perform a subgroup analysis of our data to see if certain groups of people that have better pain reduction with the Active TENS unit and an analysis of risk factors that might contribute to pain with Intradetrusor Onabotulinumtoxin A injection.

Power Calculation: Based on our baseline preliminary data and the study ‘Transcutaneous Nerve Stimulation for Pain Relief During Office Hysteroscopy’ by Lison et al (2017)(6), power calculations were performed. As estimates of the mean and variance of the pain scale we used table 2 from the Lison et al (2017) study and our preliminary data. Group sample sizes of 27 and 27 achieve 80.53% power to reject the null hypothesis of equal means when the population mean difference is $\mu_1 - \mu_2 = 4.0 - 2.0 = 2.0$ with standard deviations of 2.0 for group 1 and 3 for group 2, and with a significance level (alpha) of 0.050 using a two-sided two-sample unequal-variance t-test.

Data Analysis: The data will be analyzed using an intention-to-treat approach. In order to account for individual participant pain sensitivity profiles through the experiment, random effect longitudinal model will be adjusted to the data controlling by treatment and selected covariates at baseline.

6.2.2 Specific Aim # 2: To evaluate the effect of TENS units on participant satisfaction following cystoscopic intradetrusor onabotulinumtoxin A injection in women with OAB.

We plan to evaluate participant satisfaction on a 10 point Likert scale immediately after the procedure in participants randomized to activated TENS units and placebo TENS units.

Hypothesis: There will be a high level of participant satisfaction on a 10 point Likert scale in the active TENS group.

Interpretation: Assuming that the participant satisfaction as measured is high in the Active TENS group, then we will accept our hypothesis. If not, we plan to do a subgroup analysis to see if there are factors that contribute to higher participant satisfaction in certain groups of people in both the Active TENS and Placebo TENS group.

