Data Analysis: The data will be analyzed using an intention-to-treat approach. Baseline differences between both groups will be analyzed using Cochran-Mantel-Haenszel test with an Alpha level of 0.05. Spearman rank correlation coefficients between Likert scales will be using to assess the strength of the relationship.

7 Safety and Adverse Events

7.1 *Definitions*

Unanticipated Problems Involving Risk to Subjects or Others (UPIRTSO)

Any unanticipated problem or adverse event that meets the following three criteria:

- Serious: Serious problems or events that results in significant harm, (which may be physical, psychological, financial, social, economic, or legal) or increased risk for the subject or others (including individuals who are not research subjects). These include: (1) death; (2) life threatening adverse experience; (3) hospitalization - inpatient, new, or prolonged; (4) disability/incapacity - persistent or significant; (5) birth defect/anomaly; (6) breach of confidentiality and (7) other problems, events, or new information (i.e. publications, DSMB reports, interim findings, product labeling change) that in the opinion of the local investigator may adversely affect the rights, safety, or welfare of the subjects or others, or substantially compromise the research data, **AND**
- Unanticipated: (i.e. unexpected) problems or events are those that are not already described as potential risks in the protocol, consent document, not listed in the Investigator's Brochure, or not part of an underlying disease. A problem or event is "unanticipated" when it was unforeseeable at the time of its occurrence. A problem or event is "unanticipated" when it occurs at an increased frequency or at an increased severity than expected, **AND**
- Related: A problem or event is "related" if it is possibly related to the research procedures.

Adverse Event

An untoward or undesirable experience associated with the use of a medical product (i.e. drug, device, biologic) in a patient or research subject.

Serious Adverse Event

Adverse events are classified as serious or non-serious. Serious problems/events can be well defined and include:

- death
- life threatening adverse experience
- hospitalization
- inpatient, new, or prolonged; disability/incapacity
- persistent or significant disability or incapacity

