7.1 Stopping Rules

An interim analysis will be performed after 30 participants have undergone cystoscopic Onabotulinum Toxin A injection as part of the study. The information will also be sent to an internal reviewer (as appointment by the Mayo Clinic Obstetrics and Gynecology Department Research chair). At this point a meeting between the investigators and internal reviewer will be convened to discuss the existing data, the efficacy and any safety issues including serious adverse events that have taken place. A decision will be made as to whether to continue with the study or to prematurely terminate the study based on any safety issues.

If there are greater than 3 serious adverse (i.e. severe skin reactions, burns, muscle weakness) events reported in the 30 participants reviewed, further recruitment and administration of the TENS unit will be stopped. The study will be put on hold with the IRB and each of the adverse events will be carefully looked into for any causal relation to the TENS unit. If no causal relationship is proved then the will re-approach IRB for restarting the study.

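### Aim 2 asks what TENS does to satisfaction, but it is decided on an undefined high level in the active arm alone, with no between-arm test

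*Combined protocol and SAP*

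**What the plan says.** Section 6.2.2 states the aim as a treatment effect: "To evaluate the effect of TENS units on participant satisfaction following cystoscopic intradetrusor onabotulinumtoxin A injection in women with OAB". Section 3.6 lists the outcome as "Participant satisfaction on a Likert Scale of 1 - 10 (10 = Completely satisfied and 1 = Completely Dissatisfied", collected once, 5 to 10 minutes after the procedure. Sections 2.2 and 6.2.2 say it is evaluated in both randomised groups.

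The hypothesis names one arm: "There will be a high level of participant satisfaction on a 10 point Likert scale in the active TENS group". So does the decision rule: "Assuming that the participant satisfaction as measured is high in the Active TENS group, then we will accept our hypothesis". If satisfaction is not high, the plan goes to a subgroup search for factors linked to higher satisfaction in both arms.

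The Data Analysis paragraph of 6.2.2 states intention to treat and then names two methods: "Baseline differences between both groups will be analyzed using Cochran-Mantel-Haenszel test with an Alpha level of 0.05" and "Spearman rank correlation coefficients between Likert scales will be using to assess the strength of the relationship".

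The corresponding rule for Aim 1, in section 6.2.1, does name the comparator: "pain as measured is decreased in the Active TENS group when compared to the placebo TENS group".

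**The concern.** An effect of TENS is a contrast between active and sham. A rule that looks only at the level in the active arm cannot establish or refute that contrast. Satisfaction after an office procedure also reflects the lidocaine, the staff, relief that it is over, and the attention of being in a trial. The sham arm is there to separate these from TENS, yet it plays no part in the Aim 2 decision.

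Two features make this worse. With no cutoff for a high score, the threshold can be set after the data are seen. And no method in the section fills the gap by testing post-procedure satisfaction between arms. Satisfaction is one of only two specific aims, so a statement that the hypothesis was accepted would probably be read as evidence that TENS improves satisfaction.

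**Working it through.** **1. Is there a between-arm test of satisfaction anywhere?** Each candidate method in the plan, against what it is applied to:

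| Method | Where | Applied to | Tests satisfaction between arms? |
|---|---|---|---|
| Cochran-Mantel-Haenszel, alpha 0.05 | 6.2.2 | Baseline differences; no strata named | No: satisfaction has no baseline value |
| Spearman correlation | 6.2.2 | Likert scales; only satisfaction is called one | No: it measures association |
| Random-effects longitudinal model | Study Summary, 6.2.1 | Individual pain profiles over the procedure | No: satisfaction is a single score |
| Subgroup search | 6.2.2 | Factors for satisfaction, only if the rule fails | No |

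Cochran-Mantel-Haenszel is not a wrong method. Its row-mean-score form could compare the arms. The trouble is what it is pointed at.

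**2. The plan's own figure.** The only power figure is for pain (section 6.1): 27 per arm, difference 2.0, SDs 2.0 and 3, two-sided 0.05, unequal-variance t-test.
- Standard error = √(4/27 + 9/27) = 0.694.
- Noncentrality = 2.0/0.694 = 2.88; Satterthwaite df = 45.3.
- Power = 80.53%, as stated.

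No figure is given for satisfaction.

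**3. Inputs for an illustration.** The 27 per arm comes from section 6.1. Everything else is assumed: high means an active-arm mean at or above a cutoff c of 7 to 8, the true active mean m is 7 to 8.5, and the SD s is 1.5 to 2.5.

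**4. No TENS effect (arms identical).** By normal approximation, P(accept) = 1 − Φ((c − m)/(s/√27)). Worked case: c = 8, m = 7, s = 2 gives s/√27 = 0.385, z = 2.60 and P = 0.005.

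| Cutoff | True mean | SD 1.5 | SD 2 | SD 2.5 |
|---|---|---|---|---|
| 8 | 7 | 0.0003 | 0.005 | 0.019 |
| 8 | 7.5 | 0.042 | 0.097 | 0.149 |
| 7.5 | 8 | 0.958 | 0.903 | 0.851 |
| 7 | 8 | 0.9997 | 0.995 | 0.981 |
| 7 | 8.5 | >0.9999 | 0.9999 | 0.999 |

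When the mean equals the cutoff, P = 0.50. Bounding the scores to the 1-10 scale moves some cells: with mean equal to cutoff the range is 0.25 to 0.51, and at SD 2.5 the 0.149 becomes 0.05 and the 0.851 becomes 0.70. The spread from near 0 to near 1 remains.

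**5. Arms that differ.** Simulation, 20,000 trials per cell, 27 per arm, normal scores rounded and clipped to 1-10, Wilcoxon rank-sum with tie correction. The means are those of the latent normal scores.
- Sham better (active 7.5, sham 8.5, cutoff 7): the one-arm rule accepts in 96%, 88% and 77% of trials at SD 1.5, 2 and 2.5. Wilcoxon favours active in practically none.
- TENS better (active 7, sham 5, SD 2, cutoff 8): the one-arm rule accepts in about 0.2%. Wilcoxon favours active in 93%.
- Arms equal at 7, 7.5, 8 or 8.5: Wilcoxon at two-sided 0.05, counted only in favour of active, accepts in 2.3% to 2.8%.

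**6. What a between-arm test could detect.** A t-test has 80% power for 0.78 SD with 27 per arm (0.74 SD with 30); Wilcoxon needs about 0.80 and 0.75 SD. At SD 1.5 to 2.5 and 27 per arm, the t-test figure is 1.17 to 1.94 points. Simulated Wilcoxon power for a latent difference of 1 point (active 8) is 0.64, 0.41 and 0.28 at SD 1.5, 2 and 2.5; for 2 points it is 0.996, 0.93 and 0.80.

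**The case against.** The best defence is that this is loose drafting. The aim speaks of an effect, both arms are scored, and the analysis is by intention to treat. The Cochran-Mantel-Haenszel sentence sits under Aim 2, compares the two groups and carries the only alpha stated there. If the word baseline is a slip, the test exists. One-arm phrasing is also a habit of this protocol: the Aim 1 hypothesis is likewise worded for the active arm, without a threshold. This is a fair guess at intent. But the sentence as written does not cover satisfaction, and even on the generous reading the acceptance rule uses neither the sham arm nor any test result. For Aim 1 the rule itself supplies the comparator; for Aim 2 it does not.

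Three narrower points stand:
- The plan never says that it would reject TENS. If satisfaction is not high it fails to accept and moves to subgroups, where sham data do enter.
- Taken literally, the hypothesis concerns a level, and accepting a truly high level is no error. The error is in treating that as an answer to the stated aim.
- Reading high as a mean at or above a cutoff is an assumption; a median or a proportion is equally possible.

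None of these gives the aim a valid decision rule.

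**Conclusion.** The concern holds. As written, the Aim 2 rule does not answer the Aim 2 question, high is undefined, and no between-arm test of satisfaction is specified. This is a stated rule that leads to a wrong conclusion if followed, not merely a missing detail.

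That conclusion rests on the text alone. The probabilities are illustrations under assumed means, SDs and cutoffs and one reading of high. They show that acceptance depends on where active-arm satisfaction happens to lie relative to an unset threshold, not on whether TENS adds anything to sham. Exact cells should not be relied on.

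The scope is limited to a secondary aim with no power claim. The primary pain analysis, the sample size and data collection are untouched. It should be fixed.

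**What to change.** In section 6.2.2:

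1. Restate the hypothesis as higher satisfaction in the active arm than in the sham arm.
2. Name one between-arm test of the 1-10 score, by intention to treat at two-sided 0.05. The Wilcoxon rank-sum test is the simplest choice (a Cochran-Mantel-Haenszel row-mean-score test with rank scores is equivalent). A proportional-odds model would also serve. Choose one in advance.
3. Report the arm difference (or the odds ratio, if the model is chosen) with a 95% confidence interval. Accept the hypothesis only if the result is significant in favour of active.
4. Say that the comparison is not powered for small differences, so that a non-significant result is not read as no effect.
5. Show baseline data descriptively. If the Spearman correlation is kept, state which two variables it relates (satisfaction against mid-procedure pain is one option) and label it descriptive.

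The cost is wording only: satisfaction is already scheduled for every participant. The change should precede any unblinded look at satisfaction. The review after 30 participants, under Stopping Rules, is to "discuss the existing data, the efficacy and any safety issues". Its continuation decision rests on safety, but if satisfaction by arm has already been seen, the new comparison should be labelled post hoc.

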Participants will be randomized to two groups using a computerized sequence generator based on permuted block randomization (1:1 allocation ratio) on the day of the procedure by the registered nurse (RN) taking care of the participant. Participants in Group 1 will receive an Activated TENS unit for pain control. Participants in Group 2 will have a Sham, inactive TENS unit for pain control. Both groups will be blinded to the type of TENS unit received. The nursing team taking care of the participant will know about the randomization. The care providers performing the procedure and the study coordinator will not be notified about the randomization.

On the day of the procedure, after baseline questionnaires and randomization, the participant will receive intraurethral lidocaine jelly as part of the standard pain control measures. Her bladder is then emptied using a Foley Catheter, and at the same time the bladder is then backfilled with 30 ml (300 mg/30 ml) of 1 % plain lidocaine solution. A waiting period of 30-50 minutes duration is allowed for the intravesicle lidocaine to take effect. During this wait period, participant is asked to lie supine for 10-15 minutes, then roll to the left side for 10-15 minutes and then to right side for about 10-15 minutes.

The participant, the provider taking care of the participant and the study coordinator assigned to the study will be blinded to the randomization. Both groups of participants will receive the TENS unit electrode placement during this wait period by the RN.

In participants randomized to the Active TENS group, the TENS unit will be initiated on standard setting (see ‘TENS, Electrode Placement, and Settings’) 5 minutes before starting the cystoscopy and will last the duration of the cystoscopy. The device intensity (amplitude) will be individually adjusted to each participant’s maximum sensory level, which is the strongest reported tingling feeling without pain and muscle contractions and kept at this setting for the duration of the procedure.

Participants randomized to the Sham TENS group will not receive the TENS therapy. Instead, they will receive electrode placement followed by initiation of the TENS unit until the participant feels the tingling sensation, following which the TENS unit will be immediately turned off by the RN. The participant will be notified by the RN that the TENS stimulus has been turned down such that they are not able to feel the tingling sensation anymore.

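### Section 3.6 lists 12 pre-treatment characteristics as secondary endpoints, and Section 6.2.2 applies its only between-group test to baseline differences instead of to satisfaction

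*Combined protocol and SAP*

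**What the plan says.** The list headed "3.6 Secondary Endpoints" has 13 bullets. The first is "Participant satisfaction on a Likert Scale of 1 - 10", collected 5 to 10 minutes after the procedure. The other 12 are PHQ-9, GAD-7, history of sexual abuse, history of chronic pelvic pain, demographics, co-morbidities, medications, smoking, illicit drug use, chronic pain, number of previous injections and previous OAB therapies. The demographics bullet holds four variables: "Participant Demographics: Age, Ethnicity, Basal Metabolic Index (BMI), Insurance".

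Section 5.2 puts the questionnaires before treatment. Lidocaine, and then the TENS electrodes, follow "On the day of the procedure, after baseline questionnaires and randomization". Under Section 3.6 most of the remaining items come from the medical record.

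The data-analysis paragraph of Section 6.2.2 (Specific Aim 2, satisfaction) states intention to treat and then: "Baseline differences between both groups will be analyzed using Cochran-Mantel-Haenszel test with an Alpha level of 0.05". It closes with Spearman correlations between Likert scales. It names no variable for the Cochran-Mantel-Haenszel test and no other test between arms.

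Section 3.5 lists the pain score taken before the procedure as one of three primary endpoints.

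**The concern.** An endpoint is something that treatment could alter. Depression score, age or number of earlier injections cannot respond to a stimulator switched on five minutes before cystoscopy. Listing them as secondary endpoints invites a comparison between arms, and Section 6.2.2 appears to supply one at 0.05.

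Two things are at stake. First, a chance imbalance in one of these items could be read as a secondary result. Second, and of more practical weight, the comparison that Aim 2 needs is absent. The aim is the effect of TENS on satisfaction, yet the stated test is directed at baseline. The aim's hypothesis and interpretation are worded around the level of satisfaction in the active arm, so they do not supply the comparison either.

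**Working it through.** **The plan's own figure.** Section 6.1 gives 80.53% power with 27 per arm, a difference of 2.0 and SDs of 2 and 3, using a two-sided unequal-variance t-test at 0.05.
- Standard error = √(4/27 + 9/27) = √(13/27) = 0.694.
- Noncentrality = 2.0/0.694 = 2.88.
- Welch degrees of freedom = 26 × 13²/(4² + 9²) = 4394/97 = 45.3.
- The noncentral t distribution gives 80.53%, which reproduces the figure. Allowing for 10% dropout, 27/0.9 = 30 per arm.

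Nothing below enters this calculation.

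**Count of baseline items.** 13 bullets − 1 (satisfaction) = 12. Splitting the demographics bullet into its four variables gives 12 + 3 = 15. Section 6.2.2 does not list what is tested, so 12 to 15 is an assumption.

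**Chance findings with independent tests.** Allocation is 1:1 by computer-generated permuted blocks (Section 5.2). If it is carried out as intended, each baseline null is true and each test at 0.05 has a nominal 5% chance of being significant. For k tests the expected number is 0.05k, and the probability of at least one is 1 − 0.95^k.

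| k | Expected number | At least one |
|---|---|---|
| 12 | 12 × 0.05 = 0.60 | 1 − 0.95^12 = 46% |
| 15 | 15 × 0.05 = 0.75 | 1 − 0.95^15 = 54% |

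**With correlation.** PHQ-9, GAD-7 and the two pain histories are unlikely to be independent. A simulation drew 200,000 sets of 12 equally correlated normal test statistics and counted a set if any exceeded 1.96 in absolute value. The probability of at least one was 43% at correlation 0.2 and 32% at 0.5. Both correlations are assumptions. The expected number stays at 0.60, because it does not depend on correlation.

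**Between-arm test for satisfaction.** Section 6.2.2 names two procedures. The Cochran-Mantel-Haenszel test is assigned to baseline differences. Spearman correlation measures association between scales and does not compare arms. That leaves none for satisfaction.

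**The case against.** The strongest reply is that the Cochran-Mantel-Haenszel sentence is a slip. It sits in the satisfaction analysis, names no baseline variable and comes just before a sentence on Likert scales, so it may have been meant for satisfaction. That is plausible, and it is why the sentence should be reworded and not simply deleted. As written, though, it tests baseline.

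A second reply is that the label does little harm. Both aims and both hypotheses concern only pain and satisfaction, and Section 5.2 itself calls the questionnaires baseline. Section 12 promises to post results but does not say that these items will be posted as outcomes. This stands: misreporting is a risk, not a certainty.

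Third, the null is true by design only if allocation was not subverted. The treating nurse, who knows the assignment, performs the randomisation, and no concealment is described. The conclusion is therefore conditional on intact allocation.

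Two stronger readings are tempting, and the documents do not support them.

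- *The baseline p-values will choose the covariates of the pain model.* Section 6.2.1 adjusts for "selected covariates at baseline" without naming them, but that is Aim 1 and the test is in Aim 2; nothing links the two. Nor are these p-values the only result that could influence the choice: Section 6.2.1 plans a risk-factor analysis if the pain hypothesis fails, and investigators discuss efficacy after 30 participants. Even if imbalance did drive the choice, an illustrative simulation showed no inflation of type I error: 3.5% to 4.4%, against about 4.8% with prespecified covariates. It assumed 30 per arm and 12 covariates, 3 of them prognostic with coefficients 0.3 or 0.5.
- *The Cochran-Mantel-Haenszel test cannot fit.* It does not need randomisation strata. Its mean-score form handles ordered scores and can be run with a single stratum. PHQ-9 and GAD-7 also have a cut-off of 10 in Section 5.2.

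**Conclusion.** The point holds in two parts. Section 3.6 mislabels 12 of 13 items as secondary endpoints, and Section 6.2.2 directs its only between-group test at baseline differences, leaving satisfaction without one.

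The chance of at least one spurious baseline finding is 46% to 54% for 12 to 15 independent tests, and about 32% to 43% for 12 tests with correlation 0.5 to 0.2. These figures rest on intact allocation, on an assumed number of tests and, for the lower range, on assumed correlations. They describe baseline tests only and are not an error rate for pain or satisfaction. The 30 per arm and the 80.53% power are unaffected.

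**What to change.** - **Section 3.6:** keep participant satisfaction as the only secondary endpoint. Move the other 12 items to a list headed *Baseline characteristics*.
- **Section 3.5:** treat the pre-procedure pain score as a baseline value in the same way. It can still serve the change comparisons in Aim 1.
- **Baseline reporting:** describe each characteristic by arm with mean and SD, median, or counts as suits the variable, without p-values.
- **Section 6.2.2:** reword the sentence so that the between-arm test at 0.05 applies to the satisfaction score. A Cochran-Mantel-Haenszel mean-score test or a Wilcoxon rank-sum test would serve; name one.

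The cost is an edit to the text of three sections. Data collection, participants and sample size are not affected.
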